#### Victims of rape/sexual abuse

In the event that the Y-Check team discovers a case of rape or sexual abuse amongst the participants, the matter shall be referred to the District Social Development Offices, as per standard reporting guidelines set out by the Ministry of Public Service, Labour and Social Welfare.

# 7.7 Confidentiality

Strict measures will be in place to safeguard confidentiality of data. All reports, study data collection, process, and administrative forms will be identified by coded numbers only to maintain participant confidentiality.

For adolescent clients accessing the Y-Check services, at registration the clients name, sex, date of birth, address and contact phone number will be recorded in a separate log file along with their national ID number. These identifiers are required for operational purposes e.g. to provide a referral to external service. Personal identifiers on paper will be stored in a locked cabinet. Electronically kept personal identifiers will be stored in separate datasets with password protection only accessible for designated staff (for computers and servers). These measures will ensure that adolescent client information remains confidential.

Research cohort members will be allocated a unique study ID number. Identifying information will additionally be used to allow tracing of the study cohort to invite them to attend follow-up visits, qualitative interviews, or other research activities. Personal identifiers may appear on paper or electronically on appointment books, consent forms, log books, follow up lists and other listings. These listings will NOT include any (sensitive) study information (including diagnoses). Further information on data management is provided in section 5.3.

# 7.8 Data and Safety monitoring

An independent Scientific Advisory Committee will review operational performance including uptake, retention and adverse events on an ongoing basis, and will advise the study team on study conduct. Data on the uptake of each component of the study intervention will be captured electronically in all communities and used to inform adaptations to improve uptake of and access to the intervention.

Adverse events, defined as an untoward medical occurrence in an individual to whom a medicinal product has been administered including occurrences that are not necessarily caused by or related to that product, among individuals accessing the intervention, will be recorded. The products referred to include iron and folic acid supplements, fluoride varnish and SDF application, vaccinations, STI treatment, modern contraceptives, PrEP and MHH products.

Social harms are defined as any untoward social occurrences that happen to a participant as a result of their participation in the study, with examples including loss of employment, harassment by neighbours, shunned by family, rejection by partner etc. Because this study is a community-based study of a multifaceted intervention, the majority of people in the community affected by the implementation of the study will not be participants in the screening or follow-up visits, and so the definition of social harm for this study will be expanded to also include any untoward social occurrences that happen to a community, or groups or individuals within a community, as a result of implementation of the study intervention. Social harms will be monitored throughout the study (through report from those accessing the Y-Check intervention) and study staff will be trained to report these on a regular basis and to provide appropriate counselling and/or referral to appropriate resources, as needed. Staff may also become aware of social harms passively for e.g. if they live in the intervention communities, and will be encouraged to report these.

Discussion of social harms will be addressed with the SAC and with the YAG. The qualitative research to be conducted as part of the process evaluation will also explore social harms in the community. The study team will review the social harms reports monthly, or sooner, if a concerning trend or event is

identified. If the team judges an individual social harm, or a trend in social harms, to be serious or unexpected, they will work together with appropriate bodies (IRBs, YAG, SAC, Study sponsor) to determine if a response is indicated, and if so, what it should be.

Adverse events and social harms will be reported to the ethics committees according to their individual requirements.

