#### Hearing

Hearing problems will be identified using the HearScreen or HearWHO smartphone app. Participants who fail the HearScreen or HearWHO test may have the threshold of their hearing loss measured using HearTest and the nurse will check for the presence of wax using an otoscope or the smartphone app. If wax is present, then the nurse will attempt to remove the wax and then repeat the hearing test. For those who still fail the hearing test and/or where wax was not present, the participant will be referred to specialist services for further examination and potential treatment with antibiotics for chronic middle ear infection, wax removal, or hearing aid fitting.

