#### 7.4 Risk-benefit assessment

The risks and benefits of the Y-Check intervention will be described to participants and their parents/guardians during the consent process. Y-Check participants will benefit from early detection of health problems, health promotion, and the development of health-seeking behaviours. Those who choose to participate can opt out of responding to questions or completing examinations/procedures. HIV and STIs are conditions, which are associated with stigma and anxiety. The Y-Check team will provide counselling to those participants testing positive for HIV or STIs. There is also a risk of negative consequences of a parent or guardian finding out that an adolescent has a drug or alcohol problem. However, if needed, participants and their parents or guardian will have access to on-the-spot initial Y-Check counselling services and assisted referral to longer-term services. The protocols and procedures for communicating with adolescents and their families will be carefully developed in collaboration with the YAG and community stakeholders.

As for any health care, the tests and treatment provided can have side-effects that can be serious or minor. The tests could cause anxiety. The blood test could cause discomfort or a small bruise, as with any other blood test. While the possibility of this happening is low, the informed consent and assent forms will specify these risks clearly to make sure that participants are aware of the possibility. In the unlikely case of an adverse event, the team will be trained to provide care and support, as well as notify the relevant school authorities (for those seen in schools). If urgent care is required, they will be supported to attend a local health facility.

Risks will be minimized by explaining the procedures in detail to adolescents during the school sessions, as well as during the process of obtaining informed consent in schools and community venues. Staff will be trained to detect adverse events and a protocol will be in place to ensure action in the rare case that such an event occurs.

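### Section 7.8 ties adverse-event recording to receipt of a product, so medical harms of the screening tests fall outside it for participants who receive none

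*Protocol*

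**What the plan says.** Section 7.8 (Data and Safety monitoring) states which medical events are recorded. The definition begins "Adverse events, defined as an untoward medical occurrence in an individual to whom a medicinal product has been administered" and continues "including occurrences that are not necessarily caused by or related to that product". A causal link is therefore not needed, but receipt of a product is. The section then names the exposures: "The products referred to include iron and folic acid supplements, fluoride varnish and SDF application, vaccinations, STI treatment, modern contraceptives, PrEP and MHH products". That list is open-ended, but open to further products; it contains no test, examination or procedure.

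Section 7.4 (Risk-benefit assessment) takes a wider view of where harm can come from: "As for any health care, the tests and treatment provided can have side-effects that can be serious or minor". It gives examples that belong to testing alone: "The tests could cause anxiety" and "The blood test could cause discomfort or a small bruise, as with any other blood test". It then describes how staff will respond to an adverse event, with no condition that a product was given.

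Section 7.8 has a second category, social harms, which is confined to social occurrences.

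**The concern.** Screening is the exposure that every attendee shares, and most of them are minors. The visit includes a finger-prick, a jump or squat test, self-taken vaginal swabs in the community hubs, questions on violence and mental health, and a hands-on procedure in the hearing section: "If wax is present, then the nurse will attempt to remove the wax". None of these is a product. If the rule for recording medical harm asks first whether a product was received, a harm of screening is captured only when the adolescent also happened to receive one.

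The Scientific Advisory Committee's review in 7.8 and the reports to the ethics committees in 7.8 and 7.10 all use the same term, so any gap in the definition carries through to them. The study is also meant to inform wider use of check-up visits, where the harms of screening would be one of the questions asked.

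**Working it through.** No calculation in the plan is at issue. The check is to set the provisions side by side and ask who is left out.

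1. **Who must have an event recorded.** Section 7.8 covers people who have received a product, whether or not the event is related to it. It sets no time limit after the product.

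2. **Who receives a listed product.** The oral health part of section 3.7.2 plans fluoride varnish for every participant regardless of dental findings, and varnish is on the 7.8 list. Section 3.7.2 also plans menstrual products for females, and these are listed too. Someone who completes the visit as planned therefore meets the 7.8 condition. A bruise or faint from a test then counts, because relatedness is not required. With no time limit, the same person is still covered at the 4-month and 12-month visits.

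3. **Who may receive none.** There are three routes:
   - Section 3.7 allows a participant to take only part of the visit. Its own example skips the examination and laboratory tests, so for that participant the relevant harm would be distress from the questionnaire.
   - Section 7.4 allows any examination or procedure to be declined. An adolescent could have the finger-prick and the jump test but refuse the oral component.
   - In section 3.7.3 the questionnaire, physical examination and laboratory tests are Stations 2 to 4, and on-the-spot treatment comes with the nurse at Station 5. Someone who leaves because of an event at Stations 2 to 4 may never reach a product.

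4. **Is varnish for all stated consistently?** Appendix 1 lists varnish in the row for poor oral health, whereas section 3.7.2 gives it to everyone. The two should be reconciled, because coverage under 7.8 leans on this point.

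5. **Timing.** The definition describes the person, not the order of events. An event at Station 4 in someone given varnish later the same day can be read as included or as excluded. The text does not settle it.

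6. **Other recording routes.** Social harms do not cover medical events. Section 7.4 promises trained staff and a protocol for acting on adverse events, which concerns the response; it does not say that test harms are logged.

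7. **Size.** Let p be the share of screened participants who receive no listed product. The number outside the definition is 2000 × p for the main study. At p = 0 this is 0, and each percentage point adds 0.01 × 2000 = 20 people. These are people whose events would not be captured, not events. The protocol gives neither p nor an event rate, so no estimate can be made.

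**The case against.** A reader might infer that screening harms go unrecorded across the whole study, that is at 2000 check-ups and 2 × 2000 = 4000 follow-up visits, and that the study could report no harms of screening because its definition shuts them out. The documents do not support this. Varnish for all, together with a definition that includes unrelated events and has no time limit, already covers most attendees at the first visit and afterwards. The follow-up visits may also offer fewer tests (section 4.3.2). Nor does the station order by itself put every event at Stations 2 to 4 outside the definition, since 7.8 can be read as describing the person.

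The defence can add more. Section 7.4 is a risk disclosure, not a rival definition, and never expressly calls a bruise or anxiety an adverse event. Other routes might bring harms to light: exit interviews, the question on unanticipated consequences in Table 2, urgent referral for mental-health findings, and each ethics committee's own reporting requirements. The tests are low-risk, and section 3.7.4 asks that the intervention teams be held largely to public-health norms.

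Much of this stands, and it limits the point to a narrow group. It does not remove it. None of those routes is described as a record of medical harms from tests. The coverage through varnish is a by-product of the oral health plan; 7.8 does not state it, and field staff working from a list of products could easily miss it. Whether a faint at the finger-prick is recorded should not turn on whether the adolescent also accepted varnish.

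**Conclusion.** The point holds in a limited form. Section 7.8 sets a narrower scope for recording harm than the risks described in 7.4. Screening harms are outside the definition for participants who receive no listed product, and their status is unclear when the event precedes the product. For everyone else the definition already reaches them.

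This rests on three assumptions: that varnish is delivered to all who accept the oral component, as section 3.7.2 says; that 7.8 has no implied time limit; and that the adverse-event protocol mentioned in 7.4, which is not shown, does not widen the definition. The gap is near nil if nearly everyone has varnish and rises in direct proportion to the share who receive no listed product. It affects the safety record only; the primary outcome and the sample size are untouched. It is worth correcting because a stated rule is too narrow and the correction is cheap.

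**What to change.** In section 7.8, define an adverse event as any untoward medical occurrence in an individual undergoing any Y-Check test, examination, procedure or treatment, whether or not it is related and whether or not a product was given. Add the screening procedures to the named exposures: finger-prick, self-taken swab, wax removal, physical-function tests, and acute distress after screening questions. Sections 7.8 and 7.4 would then agree, and the timing question would disappear. Align the report form with the new wording.

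The cost is about a sentence of protocol text, a change to the form, and a few more minor events to record. No clinical rule, outcome or sample size changes.

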# 7.9 Clinical management during and post-study

Clinical management for conditions identified during the check-up visits e.g. anaemia, STI, HIV etc. will follow national guidelines. Where no national guidelines exist we will follow international guidelines issued by WHO. For those who test positive for HIV, treatment will be provided through the national health systems according to national guidelines which stipulate that all individuals who test HIV-positive are eligible for ART regardless of age or disease stage.

#### 7.10 Ethical Review

Approval to conduct this study will be obtained from the MRCZ, the BRTI IRB and the LSHTM Ethics Committee. Where there is disagreement or discordant IRB requirements the condition providing the highest level of human subject protection will be implemented. Adverse events will be reported on a regular basis according to the individual requirements of these IRBs.

## 8. Administrative Procedures

# 8.1 Regulatory approvals

The study will be conducted in accordance with the principles of the Declaration of Helsinki and in full conformity with relevant regulations and with the ICH Guidelines for Good Clinical Practice (CPMP/ICH/135/95) June 1996. Prior to implementation of this protocol, and any subsequent full version amendments, the protocol and the consent form(s) will be approved by the MRCZ, the LSHTM Ethics Committee and the BRTI IRB. The PI will register as a foreign researcher with the RCZ.

#### 8.2 Indemnity

LSHTM carries Clinical Trial/Non-Negligent Harm Insurance and Medical Malpractice Insurance applicable to this study.

#### 8.3 Study monitoring

An independent Scientific Advisory Committee will oversee study progress and advise the study team. The study may be subject to audit by the London School of Hygiene & Tropical Medicine under their remit as sponsor, the Study Coordination Centre and other regulatory bodies to ensure adherence to GCP.

#### 8.4 Protocol compliance

The study will be conducted in full compliance with the protocol. The protocol will not be amended without prior written approval by the PI. All protocol amendments will be submitted to and approved by the MRCZ, the LSHTM Ethics Committee and to the BRTI IRB prior to implementing the amendment. At the end of the study the MRCZ will be notified of the completion of the study (using the FORM 105- study termination form) and a final study report will be sent to the MRCZ.

## 8.5 Maintenance of records

The study team will maintain and securely store complete, accurate and current records throughout the study. All study records will be maintained for five years after the end of the study, as per MRCZ regulations. Study records include including protocol registration documents, all reports and correspondence relating to the study and documentation related to study participants (including informed consent forms, locator forms, case report forms, notations of all contacts with the participant, and all other source documents).

# 8.6 Use of data and publications

All processes related to data use will follow the principles of Good Clinical Practice.

Publication of the results of this study will be governed by the requirements of the UKRI open access policy. All publications will be made available through PubMed Central (PMC) and Europe PMC as soon as possible and within six months of the journal publisher's official date of final publication. Where possible (and when an open access fee is paid), research papers will be licenced a Creative Commons Attribution licence (CC-BY).

# **Appendix 1: Conditions with correct management and subsequent outcomes**

Condition/risk behaviour	Screening tool	Primary Outcome: Appropriate on the spot care or complete appropriate referral		Secondary clinical or behavioural outcomes
		Appropriate on the spot care	Complete appropriate referral	
Psychosocial issues (home environment, education/employment, violence etc.)	Questions from HEEADSSS 	Counselling +/- referral	Attend first meeting with social services	Severity of psychosocial issue
Alcohol, tobacco and substance use	ASSIST-Y 	Brief intervention +/- referral	Attend first meeting with counsellor	Alcohol use Tobacco use Substance use
Common mental health disorders	Shona symptom questionnaire (SSQ) 	Counselling +/- referral to Youth Friendship Bench if SSQ score >=8. If 'red flag' refer to nearest health facility.	Attend first meeting of Youth Friendship Bench	Severity of symptoms
Low levels of physical activity	Questions from HEEADSSS 	Counselling and advice		Level of physical activity
Poor diet	Questions from HEEADSSS 	Counselling and advice +/- referral	Attended first appointment at food supplementation services	Frequency of fruit and vegetable intake Frequency of sugary beverage intake
Underweight	MUAC, BMI, BVI	Counselling and advice +/- referral	Attended first appointment at food supplementation services	MUAC/BMI/BVI
Overweight	MUAC, BMI, BVI	Counselling and advice		MUAC/BMI/BVI
Anaemia	Hemocue	Iron and folic-acid supplementation (3 months supply) if anaemic. If severely anaemic (<8g/dl) refer to health facility.	Attended first appointment at health facility.	Anaemia

Poor oral health	Questions on oral health.  Visual inspection.	Advice, gift of toothpaste and toothbrush, fluoride varnish application +/- SDF application +/- referral	Attended first appointment at dentist	Reported pain or swelling. Frequency of tooth brushing
Uncircumcised	Question on circumcision status. Visual inspection.	Referral for VMMC (males only)	Attended first VMMC referral appointment.	Circumcised
Unprotected sex	Question (s) on sexual activity	Risk reduction counselling, Provision of condoms, Provision of modern contraceptives (emergency contraception, depot injections, oral contraceptive pill) (females only)  PrEP (females only)		Frequency of unprotected sex  Modern contraceptive use (females)  PrEP use (females)
HIV positive	HIV oral mucosal self- test +/- confirmatory blood-based RDT	Counselling + referral	Enrolment in ART programme	ART adherence
STI (CT, NG, TV)	CT/NG test on urine sample, TV test on self-taken vaginal swab	Treatment		STI (CT, NG, T)
Incomplete immunisation	Question on HPV immunisation history. Review of vaccination card.	Immunise +/- referral	Attend referral appointment for second vaccine dose	HPV immunisation
Visual impairment	Peek Acuity or Snellen Tumbling-E	Refer to specialist if <6/12 level in either eye.	Attends first eye appointment	Visual impairment Reported frequency of wearing glasses
Hearing impairment	HearScreen smartphone app +/- HearTest	Inspection for presence of wax and wax removal. Refer to specialist	Attends first hearing specialist appointment	Hearing impairment Reported frequency of wearing hearing aid
Physical impairment	Questions on physical impairment.	Refer to specialist	Attends first appointment with specialist	Upper and lower limb impairment

	Jump or squat test			
	Functional reach test			
Uncontrolled Epilepsy	Questions on	Refer to specialist	Attends first appointment with	Controlled epilepsy
	experience of		specialist	Reported frequency of
	convulsions			taking epilepsy medication
Pre-hypertension	Blood pressure	Counselling and advice if lowest	Attended first referral	Blood pressure
	measured using digital	systolic reading 120-129mmHg +/-	appointment	
	sphygmomanometer	referral if suspected hypertension		
		(Lowest systolic reading >130mmHg)
